9.2 Event Reporting

Certain events, in addition to recording on the study's eCRF's, will require prompt reporting to the University of Minnesota according to the table below:

Agency	Criteria for reporting	Timeframe	Form to Use	Submission information	Copy to:
U of MN IRB	Events requiring prompt reporting including, but not limited to unanticipated death of a locally enrolled subject(s); any unanticipated adverse device effect, new or increased risk; any adverse event that require a change to the protocol or consent form or any protocol deviation that resulting in harm refer to http://www.research.umn.edu/irb/forms.html	within 5 business days of discovery	Report Form	[contact]	SAE Coordinator [contact]

10 Data Collection and Study Monitoring

10.1 Data Management

This study will report clinical data using The Online Enterprise Research Management Environment (OnCore™), a web based Oracle® database utilizing study specific electronic case report forms. Key study personnel will be trained on the use of OnCore and will comply with protocol specific instructions embedded within the OnCore forms. Patient demographics, patient specific study treatment calendars, adverse events, reporting of deaths, and other information will be placed in OnCore. The iScorEB results will be recorded in the BMT database. All biopsy results and photographs will be maintained and stored under the supervision of the PI.

10.2 Case Report Forms

Participant data will be collected using protocol specific electronic case report forms (e-CRFs) developed within OnCore based on its library of standardized forms. The e-CRF will be approved by the study's Principal Investigator and the Biostatistician prior to release for use.

10.3 Data and Safety Monitoring Plan (DSMP)

The study's Data and Safety Monitoring Plan will be in compliance with the University of Minnesota Masonic Cancer Center's Data & Safety Monitoring Plan (DSMP), which can be accessed at <https://z.umn.edu/dsmp>

For the purposes of data and safety monitoring, this study is classified as moderate risk. Therefore the following requirements will be fulfilled:

- The Masonic Cancer Center Data and Safety Monitoring Council (DSMC) will review the trial's progress twice yearly.
- The PI will comply with at least twice yearly monitoring of the clinical protocol by the Masonic Cancer Center monitoring services.
- The PI will oversee the submission of all reportable adverse events per the definition of reportable in section 9.2 to the Masonic Cancer Center's SAE Coordinator and the University of Minnesota IRB.

In addition, at the time of the continuing review with the University of Minnesota IRB, a copy of the report with any attachments will be submitted to the Cancer Protocol Review Committee (CPRC).

11 Outcome Measures

Multiple wounds may be treated for each patient. The primary outcome measure is the percentage of grafts successfully treated. Therefore, the experimental unit for this pilot study will be the wound, not the patient. If the body surface area affected by the wound is at least 50% lower at 12 weeks relative to baseline, the graft will be considered successful. For the purposes of this study only the initial treatment session (of up to 3 wounds for treatment and an equal number of control wounds) will be used for fulfilling the primary and secondary study endpoints.

Healing of wounded skin is a fairly stereotypic process in simple wounds, but becomes complicated and complex in the setting of multiple factors converging on the status of a wound at specific time. This includes: type of EB, gene mutation causing the RDEB or JEB, polymorphisms in modifier genes (such as enzymes that recycle skin extracellular matrix), infection and inflammation (local and systemic), HCT factors (age, graft, type of conditioning, physical and immune complications), and resulting hematopoietic and skin chimerism.²⁰⁻²⁴

Therefore, we will use several measures in the recipient (the patient with EB) to establish a template for the most accurate and unbiased evaluation of benefits associated with epidermal grafting, as follows:

[1] Physical exam. Comprehensive evaluation will be performed at 0 (i.e., before) grafting, at 6 (remote visit via phone assessment possible if physician and family agree travel to U of MN not clinically indicated) and 12 weeks, and 1 year after grafting.

[2] Photographs. In addition to photographs taken with an iPad or similar device, a specialized camera or photograph with standard measuring device in picture may be used at these four time-points (0, 6 and 12 weeks and 1 year after grafting) per PI discretion to allow for quantitative assessment of wound size over time. Weekly photographs will also be requested as able until the week 12 visit to assess healing and for any adverse events.

[3] iscorEB. A validated, EB-specific scale used to capture data regarding quality of life, pain and itching will be obtained at 0, 6 and 12 weeks and 1 year after grafting.^{20,23,24}

[4] Donor assessments. Follow up physical assessments, adverse event assessments, and photos can be performed remotely at donor's home clinic (if physical exam is clinically indicated) or with UMN physician (i.e. telephone call, skype, etc.), if donor is not able to return.

Of note, all these procedures are fully operational and have been used extensively to assess clinically relevant and actionable data in more than 50 individuals from families with RDEB and JEB evaluated at the UMN over last 8 years. As we have established immune tolerance after successful grafting of bone marrow or umbilical cord blood, we have been developing approaches to leverage this immune tolerance in local therapy. We plan to use Cellutome® as a complementary therapeutic measure for difficult to heal erosions after hematopoietic cell transplantation (Arm A) or in autologous setting for transfer of mosaic skin (Arm B). As the immune system of the recipient will "see" such skin grafts as "self" this is an elegant way of clinical application of acquired immune tolerance in transplantation biology.

12 Statistical Considerations

This is a pilot study with the purpose of determining preliminary efficacy and safety measures of epidermal skin grafting in EB patients. Arm A (graft from hematopoietic stem cell donor) and Arm B (self-donor) will be analyzed separately.

After 1 year on study, patients may re-enroll on the trial. These will be considered new subjects (each enrollment counts separately). Allogeneic recipient re-enrollments will be considered Arm C (treatment plan identical to Arm A) and self recipient re-enrollments will be considered Arm D (treatment plan identical to Arm B). Arm C and Arm D will not contribute to primary or secondary outcomes, but a descriptive summary of Arms C and D will be performed separately.

12.1 Trial Size

Target accrual is 25 patients on arm A and 10 subjects on arm B over three years. Analysis of the primary endpoint can occur 12 weeks after the last subject begins treatment. Some secondary safety endpoints will be collected for 1 year.

Up to additional 25 patients may re-enroll in the study – these patients count toward a total study enrollment goal of 60 but only the initial enrollments will contribute to primary and secondary outcomes.

12.2 Analysis of Primary Endpoint

Each wound will be photographed before treatment, and at 6 and 12 weeks after treatment. If the body surface area affected by the wound is at least 50% lower at 12 weeks relative to baseline, the graft will be considered successful. The primary outcome measure is the percentage of grafts successfully treated as evaluated by a “blinded” reviewer.

Multiple wounds may be treated for each patient. The degree of correlation in response is unknown, but we expect that different wounds on the same patient could respond differently. Therefore, the experimental unit for this pilot study will be the wound, not the patient. If a mean of 2 wounds are treated for each enrolled patient, the 95% confidence interval of the response proportion will be as follows:

Observed response	95% CI in Arm A (50 lesions)	95% CI in Arm B (20 lesions)
25%	(14%, 39%)	(9%, 49%)
50%	(36%, 64%)	(27%, 73%)
75%	(61%, 86%)	(51%, 91%)
90%	(78%, 97%)	(68%, 99%)

12.3 Analysis of Secondary Endpoints

The iscorEB (which includes measures of quality of life questionnaire, pain and itching) will be summarized by means and standard deviations. Changes over time will be compared using Wilcoxon signed-rank tests.

12.4 Safety Monitoring

The trial will halt enrollment and be re-evaluated if a grade 4 (CTCAE v4) or higher skin related event at least possibly related to the CelluTome device or skin transplant procedures occurs in any one of the treated lesions.

13 Ethical and Regulatory Considerations

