1.7 Study Objectives

The **primary** study objective is to achieve > 50% wound closure as measured on a per wound basis within 12 weeks of skin grafting.

Secondary objectives are to:

1. assess safety, longevity and functionality of grafted skin in the recipient at 1 year
2. measure changes in quality of life (QOL) through pain, itching and general QOL questionnaire via iscorEB assessment score
3. safety and seamless, scar-free healing of the body sites of the donor from which epidermis has been harvested over the period of 1 year

2 CelluTome® Epidermal Harvesting System

The CelluTome® is a vacuum device that is applied to an area of skin and left on for approximately 30 minutes. Via gentle negative pressure, it slowly raises a series of small (millimeters in diameter), thin epidermal skin grafts that are then sheared off via a disposable blade within the apparatus. The grafts then adhere to a square of non-adhering silicone mesh dressing and are ready for grafting to another site. A similar piece of silicone mesh is then applied to the area of harvested skin as a wound dressing. Refer to appendix III for an overview of the process.

While similar devices have existed for years, the Cellutome has several novel transformative properties.¹⁶⁻¹⁹ Harvesting causes only possible mild discomfort (warmth and pressure), infrequent, mild scarring and/or hypopigmentation , and results in minimal

(if any) bleeding for the donor. Further, the device is significantly more automated and yields much more standardized grafts than prior iterations of this device. The potential for operator error or suboptimal specimens during blister grafting has been significantly diminished.

3 Study Overview

This is a single-institution pilot study to determine the capacity of immune-syntonic epidermal grafting to achieve > 50% wound closure as measured on a per wound basis within 12 weeks of skin grafting in individuals with the generalized severe forms of epidermolysis bullosa, DEB and JEB. Up to 3 uninfected regions (or infected regions if previously treated prior to grafting) will be identified for treatment with similar size wounds identified as controls if possible (no treatment).

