8.3 Patient (Self Donor – Arm B/re-enrollments Arm D)

	Prior To CelluTome Treatment	Day Of Harvest (Day 0)	Weekly Until The Week 12 Visit ³	6 Weeks And (+/- 1 Week) ⁵	12 Weeks (+/- 1 Week) ⁶	1 Year (+/- 3 Months) ⁶
Written consent	X					
Physical exam				X	X	X
Identification by physical exam and documentation of EB wounds ¹		X				
Baseline skin biopsy of unaffected (possibly revertent or mosaic) site and affected site to confirm somatic reversion ²	X					
Identification and documentation of harvesting sites	X					
Photographs of the targeted lesions, ("control" lesions, and harvest sites as able)	X anytime between baseline and harvest		X by parent or caretaker via iphone or similar device	X	X	X

	Prior To CelluTome Treatment	Day Of Harvest (Day 0)	Weekly Until The Week 12 Visit ³	6 Weeks And (+/- 1 Week) ⁵	12 Weeks (+/- 1 Week) ⁶	1 Year (+/- 3 Months) ⁶
Epidermal harvest and transfer of the epidermal micrografts to the targeted lesions		X				
Assessment of adverse events		X		X	X	X
Quality of life , itch and pain scales (iscorEB) ²	X anytime between baseline and harvest			X	X	X
Research skin biopsies ⁷			X			

1 – a maximum of 3 EB regions will be identified for treatment with additional wounds considered controls (as able). If there are no significant side effects, control wounds and/or other wounds may be treated after a minimum of 12 weeks of observation after the initial grafting per section 6.4.

2 –testing/procedures may be waived, if performed recently as part of follow-up on an EB treatment protocol (i.e. MT2009-09 or MT2015-20) or as standard of care, if the results are available for this study. Will attempt collection of full iscorEB at annual visits in accordance with standard of care, but at minimum, patient portion is requested for analysis of pain and itch.

3– If possible

4 – footnote deleted

5 - May be conducted remotely through UMN provider or the patient's home/local provider if physical assessment indicated and the patient is unable to return to UMN

6- Ideally at UMN site unless patient is absolutely unable to return, in which case local assessment should be completed with results sent to the PI and study staff

7 – Two 4mm punch biopsies (optional) at a grafted site to examine immunofluorescence, electron microscopy, at time of routine sedated procedure during the 1-year follow-up time period.

9 Adverse Event Monitoring, Recording and Reporting

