9.1 Event Monitoring/Documentation of Donor Sites and Recipient Sites

Event monitoring will focus on: 1) the areas from which the skin cells are harvested and 2) the sites to which the skin cells are applied for signs of poor healing (inflammation, sloughing of skin) with or without systemic fever.

Any adverse event, CTCAE v 4 \geq grade 3 and felt to be at least possibly related to the epidermal grafting procedure will be documented in OnCore. The trial will halt enrollment and be re-evaluated if a grade 4 (CTCAE v4) skin related event occurs in any one of the treated lesions per section 12.4 and is at least possibly related to the epidermal grafting procedure.

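### The only stated enrolment halt covers treated lesions, so a related grade 4 or higher skin event at a donor or self-donor harvest site does not trigger it

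*Combined protocol and SAP*

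**What the plan says.** Section 12.4 contains the only enrolment-halting rule in the protocol. One skin-related event of CTCAE v4 grade 4 or higher stops enrolment and prompts re-evaluation if it is "at least possibly related to the CelluTome device or skin transplant procedures occurs in any one of the treated lesions". Section 9.1 restates the rule and defers to it: enrolment halts "if a grade 4 (CTCAE v4) skin related event occurs in any one of the treated lesions per section 12.4". Both versions carry the same location limit.

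The same Section 9.1 directs event monitoring at two places: "1) the areas from which the skin cells are harvested and 2) the sites to which the skin cells are applied". The third secondary objective in Section 1.7 is "safety and seamless, scar-free healing of the body sites of the donor from which epidermis has been harvested over the period of 1 year". Section 4.2 requires skin donors to be healthy and more than 2 years old. The donor is the original transplant donor in Arm A and the patient in Arm B.

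**The concern.** The halting rule protects one of the two sites where the procedure can cause harm. A serious related skin event in a grafted wound stops the trial after a single case. The same grade of event on the skin from which the graft was taken does not, although that skin may belong to a healthy child who receives no treatment for themselves under this protocol.

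What is at stake is participant protection: further donors and self-donors could be harvested before anyone is required to reconsider the procedure. No endpoint, estimate or confidence interval depends on this.

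**Working it through.** The plan gives no figure for this point, so the check is mainly of wording, followed by a simple count of who is affected.

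**Is a harvest site a treated lesion?**

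- Section 6.1 uses the word treated for wounds chosen for grafting, in contrast to untreated control wounds.
- The photograph row of the Section 8.3 schedule lists targeted lesions, then control "lesions, and harvest sites as able". Harvest sites are a separate item from lesions.
- Section 9.1 numbers harvest areas and recipient sites as separate monitoring targets.
- Section 6.2 requires Arm B grafts to come from skin that has never blistered, so harvest skin is by design not a lesion.

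Read literally, harvest sites are outside the rule.

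**Was the exclusion intended?** Probably not. The relatedness clause in Section 12.4 names the CelluTome device. Section 2 describes that device as raising "thin epidermal skin grafts that are then sheared off via a disposable blade within the apparatus", so it acts directly on harvest skin. The relatedness clause reaches harvest-site harm and the location clause then removes it.

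**Do the two versions of the rule differ?** Section 9.1 says grade 4 and refers to the grafting procedure. Section 12.4 says grade 4 or higher and refers to the device or the transplant procedures. Because Section 9.1 defers to Section 12.4, this is editorial and does not change the scope.

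**What else would act on a harvest-site event?**

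| Safeguard | Section | Automatic halt stated? |
|---|---|---|
| Related events of grade 3 or higher recorded in OnCore, with no location limit | 9.1 | No |
| IRB report within 5 business days for "any unanticipated adverse device effect, new or increased risk" and similar events | 9.2 | No |
| Limits on further sessions or re-enrolment for that patient | 6.4 | No |
| Data and safety monitoring council reviews "progress twice yearly" | 10.3 | No |

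**How many people and sites fall outside the trigger?**

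- Inputs: 25 patients in Arm A and 10 in Arm B over three years (Section 12.1); at most 3 harvest sites per sitting (Section 6.3); a planned mean of 2 wounds per patient (Section 12.2).
- People harvested at first enrolment, assuming each Arm A patient has a different donor: 25 + 10 = 35.
- First-session harvest sites: minimum 35 × 1 = 35; maximum 35 × 3 = 105. Assuming one harvest site per wound at the planned mean, 35 × 2 = 70.
- Later sessions and re-enrolments are not counted.

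**How many could enrol before another body acted?**

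- Planned accrual: 35 / 36 months = 0.972 per month.
- If the first response is the next scheduled council review, with reviews evenly spaced 6 months apart: 0.972 × 6 = 5.83. Of these, 25/36 × 6 = 4.17 are in Arm A, each with a new donor, and 10/36 × 6 = 1.67 are in Arm B.
- If the IRB pauses enrolment as soon as a 5-business-day report arrives (about 7 days, or 0.23 month): 0.972 × 0.23 = 0.22.
- Range: about 0 to 6.

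No probability of such an event is calculated, because the documents give no rate of serious harvest-site events.

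**The case against.** The strongest reply is that this is a drafting point with little practical consequence. Section 7.1 expects no significant donor side effects. The September 2018 interim summary in Section 1.5 reports no scarring in any donor. Against that background, a grade 4 harvest-site event would very likely count as unanticipated or as a new risk and so go to the IRB within 5 business days. The upper end of 6 further enrolments is then unlikely. Planned accrual may also overstate the pace: the interim summary describes 9 Arm A subjects and no one treated on Arm B. Finally, Section 10.3 relies on an institutional monitoring plan, cited only by link, that may contain its own suspension powers.

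Much of this stands. The realistic number of extra enrolments is probably nearer the low end, the event is probably rare, and the unseen plan could narrow the gap.

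It does not remove the point. Section 9.2 creates a duty to report and does not say that enrolment stops. Nine Arm A subjects are too few to exclude a rare event, and there was no experience at all with self-donors. A low expected rate is also a weak reason to leave sites out: a rule triggered by one event exists for rare, serious surprises, and the protocol already accepts that logic for wounds.

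**Conclusion.** The concern holds. As written, a related skin event of grade 4 or higher at a harvest site does not automatically halt enrolment, while the same event in a grafted wound does. The rule is stated, but its scope does not match the protocol's own monitoring targets, its donor-safety objective or its reference to the device.

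The gap covers all 35 planned first enrolments at their harvest sites. Its cost in further enrolments is about 0 to 6, given accrual at the planned pace and evenly spaced council reviews, and depending on which body acts first. Confidence is high about the scope of the rule. What would happen in practice is less certain, because the institutional monitoring plan cannot be seen and the investigator, the council or the IRB could pause the trial at their discretion. This should be corrected, but it does not threaten the trial's results.

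**What to change.** In Section 12.4, change the location phrase so that the rule applies to an event *in any treated lesion or any harvest site (donor or self-donor)*. Replace the halting sentence in Section 9.1 with the amended Section 12.4 sentence, so that grade, relatedness and location read the same in both places.

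The cost is one phrase and one matching sentence. No procedure is added, because Sections 8.2 and 8.3 already schedule adverse event assessments for donors and self-donors. The downside is a possible extra enrolment pause after a rare, serious event.

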13.1 Conduct of the Study

The study will be conducted in accordance with the appropriate regulatory requirement(s). Essential clinical documents will be maintained to demonstrate the validity of the study and the integrity of the data collected. Master files should be established at the beginning of the study, maintained for the duration of the study and retained according to the appropriate regulations.

13.2 Ethical Considerations

The study will be conducted in accordance with ethical principles founded in the Declaration of Helsinki. The IRB will review all appropriate study documentation in order to safeguard the rights, safety and well-being of the participants. The study will only be conducted after IRB approval has been obtained. The protocol, written consent document, safety updates, annual progress reports, and any revisions to these documents will be provided to the IRB by the investigator.

Appendix I – Eligibility Checklist – Patient/Recipient

Study of Epidermal Grafting Using the CelluTome® Epidermal Harvesting System for the Treatment of Individual Lesions in Persons with Epidermolysis Bullosa

Eligibility Checklist – page 1 of 1

Participant initials Patient ID (assigned in OnCore)

INCLUSION CRITERIA

A “NO” response to any of the following disqualifies the participant from study entry.

		Yes	No
1	Diagnosis of Dystrophic Epidermolysis Bullosa (RDEB) or Junctional Epidermolysis Bullosa (JEB) with at least one wound, visibly free from infection and meets the eligibility for Arm A or Arm B		
2	 Cell harvest from previous HCT donor (Arm A) – meets all of the following: - At least 6 months after HCT with donor hematopoietic chimerism - Peripheral blood donor chimerism should be measured within 21 days of grafting and be \geq 5% and stable. Stability of chimerism will be determined by the protocol team and based on 3 peripheral blood chimerism values at least 1 month apart off immune suppressive therapy - Original transplant donor is available and willing to be the epidermis donor		 or check if not applicable 
3	 Self-donation (Arm B) – meets all of the following: - Proven somatic reversion - Site for skin grafting free of cellulitis and any other clinically evident abnormalities - Meets eligibility for Donor (appendix II)		 or check if not applicable 
4	Insurance pre-authorization for procedure		 or check if not applicable 
5	Voluntary written appropriate consent (Arm A patient or Arm B)		

Having obtained consent and reviewed each of the inclusion/exclusion criteria, I verify that this participant is eligible.

Signature of enrolling researcher

Date

